### **8.3 Demographics and Other Baseline Characteristics**

Descriptive summaries of the demographic and other baseline characteristics will be completed for the ITT and PP population.

Descriptive summaries of demographic and other baseline conditions will include:

- Demographics and baseline data (age, sex, race, height, weight, BMI, body surface area (BSA), smoking status, alcohol consumption, ECOG performance status)

- Tumor specific baseline characteristics: FcγRIIa allotypes, FcγRIIIa allotypes, p16 status, HPV status, EGFR expression, tumor location (oral cavity and oropharynx vs. other locations), stage of disease (locally recurrent vs. metastatic disease), EGFR pre-treatment (EGFR treatment naïve vs. EGFR treatment as part of multimodal treatment)
- SCCHN diagnosis and history
- Prior anti-cancer therapies (drug therapies, radiotherapy, surgeries)
- Echocardiogram (ECHO)/multiple-gated acquisition scan (MUGA) assessment
- Baseline physical examination
- General medical history
- Baseline signs and symptoms
- Prior medication
- Concomitant medication (at baseline / started after baseline / taken during study)
- Premedication

*Baseline physical examination:* Incidence of abnormalities will be summarized by body system.

*Medical History:* Medical history will be coded using the Medical Dictionary for Regulatory Activities (MedDRA Version 16 or newer). Incidences of findings in medical history will be summarized by system organ class (SOC) and preferred term.

*SCCHN diagnosis and history:* Months since initial diagnosis, months since most recent recurrent/metastatic diagnosis, American Joint Committee on Cancer (AJCC)/Union for International Cancer Control (UICC) staging at initial diagnosis, location of primary squamous cell carcinoma, metastatic disease and TNM classification at initial diagnosis will be displayed.

If the reported diagnosis dates are incomplete (year or year and month only), intervals will be calculated using the midpoint of the described period (15th in case of missing day only, 1st of July in case of missing day and month).

*Baseline signs and symptoms:* The number and percentage of patients with at least one baseline sign/symptom. Further details of the respective signs and symptoms will be listed.

*Prior anti-cancer therapies:* The number and percentage of patients with at least one prior therapy by type of therapy.

*Prior and concomitant medication:* All medication will be coded using the WHO-DRUG dictionary September 2013 edition (or newer). Incidences of prior and concurrent medications will be summarized by ATC level 2 and ATC level 4 if applicable.

Concomitant medication is defined as a medication other than study drug that was administered during the treatment period. The treatment period is defined as the time from day of first treatment to the EOS visit. Medication that has been classified as

premedication will be analyzed separately. Additionally the number of corticosteroids applications per patient will be analyzed.

Prior medication is defined as medication which was discontinued before start of study treatment. Medication which was started after the treatment period will be listed but not analyzed otherwise.

If the start date and stop date of medication are partially or completely missing, a medication will be assumed to be concomitant if it cannot be definitely shown that the medication was not administered during the treatment period. Missing dates will not be replaced.

Thus, the following approach will be taken for exclusion from concomitant medication because of discontinuation before start of treatment:

- If stop day is missing but month is complete, medication will only be excluded from concomitant medication if stop month is before month of treatment start.
- If stop day and month are missing but year is complete, medication will only be excluded from concomitant medication if stop year is before year of treatment start.
- If stop date is completely missing, medication will not be excluded.

For exclusion from concomitant medication because of late start after end of treatment period:

- If start day is missing but month is complete, medication will only be excluded from concomitant medication if start month is after end month of treatment period.
- If start day and month are missing but year is complete, medication will only be excluded from concomitant medication if start year is after end year of treatment period.
- If start date is completely missing, medication will not be excluded from concomitant medication.

#### **8.4 Analysis of Exposure**

The following variables will be summarized descriptively for the SAF population.

- Number of combination treatment cycles
- Number of infusions of CetuGEX™/cetuximab
- Overall treatment duration [weeks] for CetuGEX™/cetuximab
- Treatment duration [weeks] during combination treatment for CetuGEX™/cetuximab
- Treatment duration [weeks] in maintenance phase for CetuGEX™/cetuximab
- Total dose [mg] for CetuGEX™/cetuximab, cisplatin/carboplatin and 5-FU
- Dose changes/reductions: Number and percentage of dose reductions and reasons

per patient and per administration for CetuGEX™/cetuximab, cisplatin/carboplatin and 5-FU

- Dosing delays: Number and percentage of delays and reasons per patient and per administration for CetuGEX™/cetuximab, cisplatin/carboplatin and 5-FU
- Dosing interruptions: Number and percentage of interruption and reasons (AE/per-protocol/other) per patient and per administration for CetuGEX™/cetuximab, cisplatin/carboplatin and 5-FU
- Infusion rate changes: Number and percentage of infusions rate changes and reasons (AE/per-protocol/other) per patient and per administration for CetuGEX™/cetuximab
- Switches to carboplatin by reason for switch (AE/PI discretion) and first cycle of switch

Furthermore, details of study treatment termination will be tabulated, including reason for discontinuation of treatment and reason for chemotherapy termination and discontinued agent.

## 9. EFFICACY ANALYSIS

Efficacy analyses will be performed based on the treatment group the patient was randomized to unless otherwise specified.

### 9.1 Primary Efficacy Analysis

The primary efficacy analysis for PFS as assessed by the investigator will be based on the ITT population using the PFSp definition as described in Section 7.2.

A two-sided log-rank test will be used to test the null hypothesis of equal treatment effects at an overall significance level of 0.05. The Kaplan-Meier method will be used to estimate the survival functions. Median survival times together with their 95%-confidence intervals will be retrieved from the survival functions. PFS rates at 6, 12, 15 and 18 months and associated 95%-confidence intervals and graphs of the Kaplan-Meier curves by treatment arm will also be presented.

The primary efficacy analysis will not be stratified by the factors used for stratification at randomization in order to preserve the estimated power considering the high number of strata.

To investigate the influence of the stratification factor on the primary endpoint a Cox regression model will be applied as a sensitivity analysis based on the ITT population. This model will include the treatment effect and the stratification factors

- FcγRIIIa allotypes (FF, FV or VV)
- Oral cavity and oropharynx vs. other locations
- Locally recurrent vs. metastatic disease
- EGFR treatment naïve vs. EGFR treatment as part of multimodal treatment

The hazard ratios, the corresponding 95% confidence intervals and the p-values of the Wald test (using adjustment for ties according to Efron) will be presented for all factors. The Kaplan-Meier analyzes will be repeated separately within the subgroups formed by the stratification factors. Corresponding figures will combine the curves for all treatment group/factor level combinations on one page per factor. Factor levels maybe combined if the sample size per level is  $< 15$ .

Further sensitivity analyses will be done as follows

- The analyses will be repeated using the PFSs definition as described in Section 7.2
- The analyses will be repeated for the PP Population
- It has been recognized that not all sites had strictly applied modified irRC for response assessment. To investigate the influence of deviating response criteria on PFS a log rank test will performed stratifying sites according to strict adherence to modified irRC (yes/no).

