### **5. SAMPLE SIZE DETERMINATION**

Approximately 240 patients will be randomized in this study.

The log-rank test will be used to test the hypothesis that patients assigned to the CetuGEX™ arm have increased PFS compared to patients assigned to the control arm.

The sample size calculation is based on the following assumptions:

- The median PFS in the control arm is expected to be 5.6 months post randomization.
- It is expected that the median PFS in the CetuGEX™ arm can be increased to 8.4 months corresponding to a hazard ratio of 0.67.
- The overall trial duration will be approximately 36 months with an anticipated recruitment time of 24 months, anticipated treatment phase until PFS events are reached of approximately 12 months after randomization of the last patient (data

cut-off for main analysis) and ongoing follow-up for overall survival for at least 24 months after randomization of the last patient.

- Drop-outs are expected to occur at times following an exponential distribution and resulting in a drop-out rate of 10% at the cut-off for PFS analysis.
- Patients will be randomized in a 1:1 ratio.
- The overall two-sided significance level will be 0.05 and the power to be maintained 80%.

Based on these assumptions, approximately 240 patients have to be randomized to observe the required overall number of 192 events.

If the required number of events is not reached as planned after 12 months from last patient randomized, the main analysis will be postponed to obtain more events but not more than additional 6 months.

Assuming a corresponding effect on OS (hazard ratio 0.67) and a median overall survival of 10.6 months in the control group the number of survival events to be observed after a 24-months follow-up for survival will be 183.

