**15. TABLES, LISTINGS, AND FIGURES**

**15.1 Planned Table Descriptions**

The following are planned summary tables for protocol GEXMab52201. Tables will be numbered according to the nomenclature used to support the clinical study report.

Tables will be repeated according to population adding an additional table extension digit.

Table Number	Population	Table Title / Summary	Supporting Listing
14.1 DEMOGRAPHIC DATA			
14.1.1.1	All Patients	Disposition of Patients	16.2.1.1
14.1.1.2	All Patients	Analysis Populations	16.2.1.2
14.1.1.3	ITT	Major Protocol Violations by Type of Violations	16.2.2.2
14.1.1.4	ITT, PP	Stratification	16.2.1.3
14.1.2.1	ITT, PP	Demographics and Baseline Data Age, Height, Weight, MI and BSA	16.2.4.1
14.1.2.2	ITT, PP	Demographics and Baseline Data Sex, Race, Smoking Status Alcohol Consumption and ECOG Status	16.2.4.1
14.1.3	ITT, PP	Tumor Specific Baseline Characteristics	16.2.1.3
14.1.4.1	ITT, PP	SCCHN Diagnosis and History Time Since Initial Diagnosis and Time Since Most Recent Recurrent/Metastatic Diagnosis	16.2.4.6
14.1.4.2	ITT, PP	SCCHN Diagnosis and History AJCC/UICC Staging at Initial Diagnosis, Location of Primary Tumor, Location of Metastases and TNM classification	16.2.4.6
14.1.5	ITT, PP	Prior Anti-Cancer Treatments	16.2.4.10 – 16.2.4.12
14.1.6	ITT, PP	ECHO/MUGA assessment	16.2.4.3

Table Number	Population	Table Title / Summary	Supporting Listing
14.1.7	ITT, PP	Baseline Physical Examination Results by Body System	16.2.4.4
14.1.8	ITT, PP	Medical History Incidences of Findings by SOC and Preferred Term	16.2.4.5
14.1.9	ITT, PP	Baseline Signs and Symptoms	16.2.4.9
14.1.10	ITT, PP	Prior Medications Incidences by ATC level 2 and 4	16.2.9.1
14.1.11	ITT, PP	Concomitant Medication Incidences by ATC level 2 and 4	16.2.9.1
14.1.12	ITT, PP	Concomitant Pre-Medication Incidences by ATC level 2 and 4	16.2.9.2
14.1.13	ITT, PP	Number of Corticosteroids Applications	16.2.9.2

Table Number	Population	Table Title / Summary	Supporting Listing
14.2 EFFICACY DATA			
14.2.1.1	ITT, PP	Progression Free Survival (Investigator Assessment) – Primary Definition Log-Rank Test and Kaplan-Meier Analysis	16.2.6.3
14.2.1.2	ITT, PP	Progression Free Survival (Investigator Assessment) – Primary Definition Log-Rank Test and Kaplan-Meier Analysis Stratified for Strict Adherence to Modified irRC	16.2.6.3

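### The stratified log-rank test planned for sites that departed from modified irRC pools the treatment effect over both site types; no effect estimate by adherence is planned

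*SAP*

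**What the plan says.** SAP 2.2.1 and 9.1 make investigator-assessed PFS under modified irRC the primary endpoint, tested in the ITT population by an unstratified two-sided log-rank test. Among the sensitivity analyses, SAP 9.1 states: "It has been recognized that not all sites had strictly applied modified irRC for response assessment". To look into the influence of this on PFS, it plans that "a log rank test will performed stratifying sites according to strict adherence to modified irRC (yes/no".

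The table list in SAP 15.1 goes a little further. Table 14.2.1.2 (ITT and PP) covers a log-rank test and a Kaplan-Meier analysis, "Stratified for Strict Adherence to Modified irRC".

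Two other planned analyses bear on the point. SAP 9.2.1 analyses PFS by independent central reading, under irRC and under RECIST 1.1, with log-rank, Kaplan-Meier and Cox methods. SAP 11.1 cross-tabulates investigator and central best overall response. Neither is split by site adherence.

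The SAP lists no hazard ratio by adherence, no treatment-by-adherence term and, in 15.3, no figure by adherence. It does not say how many sites or patients are affected, or how, when and by whom a site is classed as adherent.

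**The concern.** The trial is open label (Protocol 9.6), and investigators decide when progression has occurred. Modified irRC (Protocol Appendix C) adds measurable new lesions to the tumor burden and requires a 20% rise in that burden, or unequivocal non-target progression. A site working to other rules can therefore record a different progression date for the same scans.

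A reader of the trial report will want to know whether the investigator-based result holds at the sites that used the protocol definition. A stratified log-rank test answers something else: whether the pooled effect survives once the two site types are allowed different baseline hazards. If the effect arose mainly at non-adherent sites, that test could still agree with the primary analysis and be taken as reassurance.

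**Working it through.** **1. The plan's own figure.** Inputs from SAP 5: "The median PFS in the control arm is expected to be 5.6 months post randomization"; the CetuGEX median "can be increased to 8.4 months corresponding to a hazard ratio of 0.67"; "Patients will be randomized in a 1:1 ratio"; "The overall two-sided significance level will be 0.05 and the power to be maintained 80" (per cent). With HR = 5.6/8.4 = 0.667, the Schoenfeld formula gives d = 4(1.960 + 0.842)² / (ln 0.667)² = 191 events, against 192 in the SAP. With the rounded 0.67 it gives 196. Power at 192 events and HR 0.667 is 80.2%.

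Expected events per patient, for PFS hazard λ, drop-out hazard η, accrual A = 24 and follow-up F = 12 months, are λ/(λ+η) × [1 − (e^(−(λ+η)F) − e^(−(λ+η)(A+F)))/((λ+η)A)]. Setting η = 0.0124 per month, so that 10% are observed to drop out ("resulting in a drop-out rate of 10% at the cut-off for PFS analysis"), gives 194 events from 240 patients. The design is reproduced, and 192 events is used below.

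**2. What the stratified test computes.** Let U and V be the log-rank score and its variance within adherent (A) and non-adherent (N) sites. The stratified statistic is z = (U_A + U_N)/√(V_A + V_N). With V_s ≈ d_s/4 for d_s events, the implied log hazard ratio is roughly the event-weighted mean of the two stratum values. The difference between strata does not enter.

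Example with events split equally: stratum hazard ratios of 1.00 and 0.45 pool to exp(½ ln 1.00 + ½ ln 0.45) = 0.671. A common hazard ratio of 0.667 pools to 0.667. The pooled result hardly separates these two cases.

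**3. How close the two tests are.** The adherent share, the baseline hazard at non-adherent sites and the stratum effects are not in the documents. They were assumed and varied in 2,000 simulated trials per scenario (240 patients, the SAP scan schedule, exponential PFS).

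Common hazard ratio 0.667, adherent shares 50% to 85%:
- The correlation of the two z-statistics is 0.993–0.994 with equal baseline hazards, 0.983–0.990 with a 1.3-fold hazard at non-adherent sites and 0.950–0.978 with 1.7-fold.
- Power is 81–83% unstratified and 80–85% stratified.
- The tests disagree on significance in 2% to 6.5% of trials.

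Different effects, 1.3-fold hazard at non-adherent sites:

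| HR adherent / non-adherent | Adherent share | Unstratified rejects | Stratified rejects | Tests disagree | Stratum contrast rejects |
|---|---|---|---|---|---|
| 1.00 / 0.45 | 50% | 83.5% | 78.2% | 6.4% | 80.5% |
| 1.00 / 0.45 | 70% | 40.5% | 31.9% | 9.5% | 74.3% |
| 0.67 / 1.00 | 50% | 33.4% | 27.7% | 9.8% | 29.5% |
| 0.67 / 1.00 | 70% | 57.5% | 51.7% | 10.2% | 27.0% |
| 0.50 / 1.00 | 50% | 75.4% | 63.0% | 14.7% | 67.5% |

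The simulated trials had about 200 to 220 events, because the cut-off was fixed at 36 months with low drop-out. The next step uses 192.

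**4. What estimates by adherence would deliver.** SE of the log ratio of hazard ratios = √(4/d_A + 4/d_N), with events split in proportion to the adherent share:

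| Adherent share | d_A / d_N | SE | 95% CI factor | Ratio detectable at 80% power | Interaction power, 0.67 vs 1.00 | 95% CI, non-adherent sites, if HR = 0.667 |
|---|---|---|---|---|---|---|
| 50% | 96 / 96 | 0.289 | 1.76 | 2.25 | 29% | 0.45–0.99 |
| 70% | 134.4 / 57.6 | 0.315 | 1.85 | 2.42 | 25% | 0.40–1.12 |
| 85% | 163.2 / 28.8 | 0.404 | 2.21 | 3.10 | 17% | 0.32–1.38 |

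The factor is exp(1.96 × SE). The detectable ratio is exp(2.80 × SE).

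**The case against.** A reader might infer that the log-rank test is the whole check and that nothing in the plan could reveal a problem. The documents do not support that.

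Table 14.2.1.2 also plans a Kaplan-Meier analysis, and SAP 7.1 presents summaries by treatment arm unless stated otherwise. Curves by arm within each site type are therefore a natural reading, and they would allow a descriptive comparison. The layout is nevertheless not stated, the table is not titled as a subgroup table in the way its neighbours are, and no matching figure is listed.

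Central-read PFS is a stronger defence. It tests the treatment effect with one set of criteria at every site. It does not show whether the investigator-based result depends on the deviating sites. Nor is it fully independent of them: investigator-called progression ends study treatment (Appendix C), and after the Final Examination only telephone follow-up is planned (Protocol 10.1.5). The central read may then be censored at the last scan.

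It can also be said that SAP 9.1 asks about influence on PFS, not on the treatment effect, and that stratification does remove a baseline shift common to both arms. That is fair. But the treatment comparison is what the primary analysis reports, so its dependence on site type is the natural next question.

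It would also go too far to call a reassuring answer built in. With strongly different effects the two tests disagree on significance in up to about 15% of trials. Even then, a disagreement does not show where the effect lies.

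**Conclusion.** The gap is real and limited. The stratified log-rank test follows from its form: it pools the effect and contains no comparison between adherent and non-adherent sites. That conclusion needs no simulation. How closely it tracks the primary test does rest on assumed shares, hazards and effects. Under a common effect the two are nearly the same. Under hazard ratios of 1.00 and 0.45, split half and half, both usually reject although the adherent sites show no benefit.

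A reader might go further and infer that deviating sites have biased the primary result or produced its effect. The documents give no data on this, and the point does not claim it. The primary test and the sample size are unaffected. What is missing is a planned estimate by adherence, and any such estimate will be imprecise.

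**What to change.** In SAP 9.1 and Table 14.2.1.2, add:

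- the treatment hazard ratio with 95% CI, and Kaplan-Meier curves by arm, within adherent and within non-adherent sites;
- a treatment-by-adherence interaction estimate with its 95% CI;
- the same split for central-read PFS under irRC;
- a written rule for classing sites as adherent, applied without reference to treatment arm or outcome, together with the number of sites and patients in each class.

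The stratified log-rank test can stay alongside these. The results should be read as estimation: a non-significant interaction would not show that the effects are alike.

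Recalculating progression dates from the sites' lesion records is a tempting addition but is not advised. Under Appendix C, non-target progression rests on the treating physician's judgement, and deviating sites may not have measured new lesions or continued scanning. The central irRC read serves that purpose better, subject to the censoring noted above.

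The cost is SAP wording, the site classification and some programming. The tumor assessments are already collected, and the primary analysis, alpha and sample size do not change.

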## **9.2 Secondary Efficacy Analysis**

Secondary efficacy analyses will be based on the ITT and PP population.

### ***9.2.1 Progression-free Survival Based on Independent Central Review***

PFS as assessed by independent centralized reading (irRC and RECIST 1.1) will be analyzed based on the PFSp definition applying a not stratified log rank test. Kaplan-Meier estimates will be presented and Cox regression models be applied as described in Section 9.1.

### ***9.2.2 Tumor Response Rates***

ORR and CBR according to different criteria (irRC, RECIST) and sources (investigator, central review) will be analyzed using Chi-square tests to evaluate the effects of treatment on ORR and CBR for the combination treatment period as wells for the entire treatment period including maintenance treatment. 95%-confidence intervals will be calculated for the rates and their treatment differences based on normal approximation.

Logistic regression models will be used to investigate the influence of the stratification factors on the response variables. These models will include the treatment effect and the randomization stratification factors. The odds ratios, the corresponding 95% confidence intervals and the p-values of the Wald test will be presented for all factors.

Absolute and relative frequencies of tumor response categories will be tabulated by time point and for the best response. Waterfall plots to illustrate individual maximum percentage change of target lesion size form baseline will be presented by treatment group.

Duration of response will be analyzed by Kaplan-Meier methods. Duration of CR will be described case by case.

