5.3 Summary of Potential Risks and Benefits

As an optimized (bio-superior) second-generation antibody of the marketed product cetuximab, CetuGEX™ has the potential to become a considerably more active anti-EGFR antibody due to its significantly higher tumor-specific ADCC activity caused by the humanized and optimized glycosylation in the production process. At the same time the removal of non-human immunogenic Gal-Gal carbohydrate structures is expected to avoid the severe hypersensitivity reactions reported to be caused by non-human carbohydrate structures of cetuximab (in some geographical regions in about 22% of patients treated with cetuximab). Furthermore, CetuGEX™ opens the chance of therapeutic activity in otherwise unsuitable patients. As the key anti-tumor mode of action, ADCC is expected to be not only pronounced in patients with Fc γ RIIIa receptor allele status VV (8 - 27 % of the population) but also in those with FF and FV allotypes (73 - 92 % of the population), while the latter show no or very low anti-tumor ADCC activity with cetuximab. Therefore extended patient populations may benefit from the potential anti-tumor activity of CetuGEX™ in the clinic. The well-known cutaneous

toxicity occurring in up to 90% of patients treated with the approved anti-EGFR antibodies cetuximab and panitumumab (Vectibix®) is clearly linked to the EGFR inhibition in the skin and correlates with the anti-tumor efficacy of the antibody. This was also observed in the patients treated with CetuGEXTM, although from first evidence with lower incidence and grade. The phase 1 study showed reasonable tolerability with an expected high incidence of IRRs (mostly grades 1 and 2, few grade 3 and no grade 4) in conjunction with a considerable activity, given the far advanced cancer population.

Immediate allergic infusion reactions are unlikely; however IRRs of low grade were very common with this compound. As in general, although it didn't happen in the reported study, any infusion reaction has the potential to occur as life threatening severe reaction like a hypertensive crisis associated with neurologic signs and symptoms, wheezing, oxygen desaturation, chest pain, headaches, rigors, and diaphoresis, cardiac emergencies, anaphylaxis, cytokine release syndrome, convulsions, or hypotension, monitoring for these events will be cautiously undertaken.

In conclusion, the benefit-risk balance is deemed positive.

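### The normal-approximation intervals in SAP 9.2.2 are adequate for whole-arm response rates, but in a subgroup as small as VV they undercover and can have zero width

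*SAP*

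**What the plan says.** On response rates, SAP 9.2.2 says that "95%-confidence intervals will be calculated for the rates and their treatment differences based on normal approximation". This applies to ORR and CBR, by investigator and by central review, for the combination phase and for the whole treatment period. No exact or score interval is named anywhere in the SAP, and there is no rule for a cell in which no patient or every patient responds.

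The planned tables (SAP 15.1) repeat frequencies with confidence intervals for ORR and CBR by FcγRIIIa allotype, tumor location, recurrence and EGFR pre-treatment (14.2.5 to 14.2.10). They do the same for CBR by p16 status and EGFR intensity (14.2.17). All are planned for both the ITT and PP populations. The table titles name no interval method, so 9.2.2 is the only instruction available.

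On size, SAP 5 says "Approximately 240 patients will be randomized in this study" and "Patients will be randomized in a 1:1 ratio". Protocol 5.3 describes "receptor allele status VV (8 - 27 % of the population"), and Protocol 5.1.1 puts FV and FF together at 80%.

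Two provisions bear on small subgroups. Protocol 13.4.3.2 makes subgroup analyses conditional on sufficient size, without a threshold. SAP 9.1 says "Factor levels maybe combined if the sample size per level is" below 15.

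**The concern.** The normal-approximation (Wald) interval takes its width from the observed proportion. When n is small or the proportion is near 0 or 1, the estimated standard error is often too small, and at 0/n or n/n it is zero. Limits can also pass 100%: 8/10 gives an upper limit of 104.8%.

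VV is the allotype most likely to produce such cells. Efficacy by allotype is a secondary objective (Protocol 6.2), and Protocol 7.2 names independence from FcγRIIIa phenotype as a goal of the study. If VV response rates carry intervals that are too narrow, a clinical study report reader will take them as better known than they are.

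**Working it through.** **The plan's own figure.** The documents give no coverage or precision figure for these intervals. The one sizing figure is 192 PFS events. With 4(1.960+0.842)²/(ln HR)² and HR = 5.6/8.4 = 0.667, this gives 4 × 7.849/0.1644 = 191, so the plan's arithmetic is sound. The 240 patients, or 120 per arm, are used below.

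**VV patients per arm.**
- 8%: 0.08 × 240 = 19.2, or about 10 per arm.
- 20% (the complement of 80% FV+FF): 48, or 24 per arm.
- 27%: 0.27 × 240 = 64.8, or about 32 per arm.

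**Rates to test (an assumption).** No ORR or CBR is assumed for this trial. The planned medians give a rough guide to CBR. Under exponential PFS, the progression-free share at time t is 2^(−t/median). Scans fall at week 6 (1.38 months) and week 12 (2.76 months). With median 5.6 months the shares are 84% and 71%; with 8.4 months they are 89% and 80%. Stable disease counts only at a minimum interval of 8 weeks (SAP 7.2), so a patient with stable disease only must reach the week-12 scan, while a responder at week 6 already counts. CBR should therefore lie roughly between the two shares. The main range used is 71–84%.

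**Formulas.** Wald: p̂ ± 1.96√(p̂(1−p̂)/n). Wilson: [p̂ + z²/2n ± z√(p̂(1−p̂)/n + z²/4n²)]/(1 + z²/n). Coverage at true rate p is the sum of the binomial probabilities of every count x whose interval contains p.

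**One case in full: n=10, p=0.80.** The Wald interval contains 0.80 for x = 5 to 9, so coverage is 0.0264 + 0.0881 + 0.2013 + 0.3020 + 0.2684 = 88.6%. Most of the shortfall is x = 10, with probability 0.8¹⁰ = 10.7%, where the interval is [100%, 100%]. The Wilson interval contains 0.80 for x = 6 to 10, so coverage is 96.7%. At 10/10 its lower limit is n/(n+z²) = 10/13.84 = 72.2%.

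**Single rates, exact coverage (Wald / Wilson, %).**

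| n per arm | p=0.71 | 0.75 | 0.80 | 0.84 |
|---|---|---|---|---|
| 10 | 79.4 / 92.7 | 92.4 / 98.0 | 88.6 / 96.7 | 81.2 / 93.9 |
| 24 | 92.3 / 96.1 | 93.9 / 97.0 | 87.3 / 95.9 | 90.6 / 95.6 |
| 32 | 91.1 / 95.1 | 91.4 / 93.7 | 89.0 / 95.2 | 89.7 / 94.9 |

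Coverage is jagged in p, and between these points Wald reaches about 95% at n=24 and n=32. Above this range it falls: at p=0.90 it is 65.0% (n=10), 91.3% (n=24) and 84.0% (n=32); at p=0.95 it is 40.0%, 70.7% and 80.2%. At p=0.45, the overall CBR reported from phase 1, Wald covers 87.3% at n=10.

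**Whole arm, n=120.** At the rates tested from 5% to 95%, Wald covers 93.5–95.5%. On a one-point grid it dips to 91.2% at 9% and 91%.

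**Treatment differences (Wald / Newcombe, %).**

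| n per arm | 0.50 vs 0.35 | 0.80 vs 0.71 | 0.89 vs 0.84 | 0.95 vs 0.90 |
|---|---|---|---|---|
| 10 | 93.0 / 93.6 | 90.1 / 95.5 | 87.2 / 97.9 | 75.3 / 99.5 |
| 24 | 93.4 / 94.2 | 94.0 / 95.1 | 93.2 / 96.3 | 90.3 / 98.1 |
| 32 | 94.0 / 94.5 | 94.1 / 95.0 | 94.4 / 96.2 | 93.3 / 98.1 |
| 120 | 94.8 / 94.7 | 94.9 / 95.1 | 94.8 / 95.1 | 94.6 / 95.8 |

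**The case against.** The strongest reply is that little depends on these intervals. ORR and CBR are secondary endpoints in an open-label phase II trial, no decision rule uses a subgroup interval, and small subgroups may be dropped or pooled. Section 9.2.2 does not mention subgroup intervals, so applying its method to those tables is the default reading, not an explicit instruction. Counting patients without sufficient data as non-responders (SAP 7.1) and the 8-week rule for stable disease both hold CBR below 100%.

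Most of this stands and limits the point. It does not remove it. The size condition has no threshold. The pooling rule is optional and is written for the PFS subgroup analyses; a level of 15 patients in total would still leave 7 or 8 per arm. No other interval method is available to whoever programs the tables.

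Three stronger readings are tempting, and the documents do not support them.
- **Coverage as low as 40%.** This needs the lowest VV share (8%) together with a true rate of 5% or 95%. No such rate is stated. The only reported CBR, from phase 1, is 45% overall and 75% per protocol (Protocol 5.2).
- **Failure of all the response intervals.** Whole-arm intervals for rates and differences hold up, as shown above.
- **A false VV-versus-FF contrast.** SAP 9.2.2 plans intervals for rates and treatment differences, not for contrasts between allotypes. Allotype enters the logistic regression there as a stratification factor.

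**Conclusion.** The point holds for small subgroups, with VV the one the documents themselves show to be small. At true rates of 71–84%, single-rate intervals labelled 95% cover about 79–92% at 10 per arm, 87–94% at 24 and 89–91% at 32. Coverage drops further above 90% at the smallest sizes, and the interval has zero width at 0/n or n/n. Treatment-difference intervals cover about 87–93% at 10 per arm and 93–94% at 24–32, and are worse where the two rates are unequal and both close to 100%.

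These figures rest on assumed response rates, on the stated VV shares and on equal numbers of VV patients per arm. The effect is confined to secondary, descriptive subgroup intervals. The primary log-rank test of PFS and the 192-event target are untouched, and whole-arm ORR and CBR intervals are adequate. The change is worth making because the SAP states the method outright and a better one costs almost nothing.

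**What to change.** In SAP 9.2.2, replace the reference to normal approximation with Wilson score intervals for single rates and Newcombe (or Miettinen-Nurminen) intervals for treatment differences. State that this applies to every ITT, PP and subgroup table of ORR and CBR. Using one method throughout avoids choosing a method after the counts are seen.

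The cost is one SAP sentence and a change of options in the SAS frequency procedure. No data, sample size or test changes. Intervals in small subgroups become somewhat wider or asymmetric, and whole-arm results barely move.
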